10.3.3.3 Pregnancy

Maternal exposure

If a patient becomes pregnant during the course of the study, the IPs should be discontinued immediately.

Pregnancy itself is not regarded as an AE unless there is a suspicion that the IP under study may have interfered with the effectiveness of a contraceptive medication. Congenital abnormalities or birth defects and spontaneous miscarriages should be reported and handled as SAEs. Elective abortions without complications should not be handled as AEs. The outcome of all pregnancies (spontaneous miscarriage, elective termination, ectopic pregnancy, normal birth, or congenital abnormality) should be followed up and documented even if the patient was discontinued from the study.

If any pregnancy occurs in the course of the study, then the Investigator or other site personnel should inform the appropriate AstraZeneca representatives within 1 day, ie, immediately, but **no later than 24 hours** of when he or she becomes aware of it.

The designated AstraZeneca representative will work with the Investigator to ensure that all relevant information is provided to the AstraZeneca Patient Safety data entry site within 1 to 5 calendar days for SAEs and within 30 days for all other pregnancies.

The same timelines apply when outcome information is available.

Paternal exposure

Male patients should refrain from fathering a child or donating sperm during the study and for 180 days after the last dose of durvalumab + tremelimumab combination therapy or 90 days after the last dose of durvalumab monotherapy, whichever is the longer time period.

Pregnancy of the patient's partner is not considered to be an AE. However, the outcome of all pregnancies (spontaneous miscarriage, elective termination, ectopic pregnancy, normal birth, or congenital abnormality) occurring from the date of the first dose until 90 days after the last dose should, if possible, be followed up and documented.

Where a report of pregnancy is received, prior to obtaining information about the pregnancy, the Investigator must obtain the consent of the patient's partner. Therefore, the local study team should adopt the generic ICF template in line with local procedures and submit it to the relevant Ethics Committees (ECs)/Institutional Review Boards (IRBs) prior to use.

11.0 STATISTICAL METHODS AND SAMPLE SIZE DETERMINATION

11.1 Description of analysis sets

All patients enrolled in the study, including those who were replaced in the run-in phase (see Section 4.4) will be included in the analysis of toxicity and efficacy.

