Both durvalumab and tremelimumab have well established toxicity profiles as a single agent and in combination. However, the combination of durvalumab tremelimumab and palliative radiation has not been previously studied, this study will include a formal safety analysis in the first 6 patients accrued. Enrollment will be halted until these first 6 patients complete the first two cycles of treatment (8 weeks), and are evaluable for acute toxicities (toxicities reported within the 1st 8 weeks after treatment initiation). Specifically, if 2 or more DLTs (Refer to Section 6.4) are observed, then, durvalumab dosing will be modified to 1500 mg IV Q6 weeks x 9 doses and tremelimumab 75mg IV Q6 weeks x 3 doses for the remaining 14 patients (fixed dosing for patients > 30kg). If 1 or fewer DLTs are observed, then an additional 14 patients will be enrolled and treated at the initial dose and schedule of durvalumab and tremelimumab. Patients in the run in phase who experience DLTs will undergo dose modifications described in Appendix 1.

Toxicities will be graded based on CTCAE v. 4 and summarized as the number and percentage of patients with each type of toxicity. Responses will be summarized as frequencies and percentages. The Kaplan Meier method will be used to estimate overall survival and progression free survival. Outcomes will be calculated from the date of study entry to the date of the corresponding event.

We will use multivariate statistics to test the hypotheses that pretreatment intratumoral immune cell phenotype and PD-L1 expression predict response to therapy, and that therapy alters systemic immunophenotype.

Sample Size Determination:

There are multiple ongoing studies in various tumor types exploring the activity of durvalumab and tremelimumab. In a published report of the combination in patients with advanced NSCLC treated on a phase Ib study, Grade 3-4 toxicity was observed in 17% of patients. Similarly, in single institution reports of SBRT with the monoclonal antibody, grade 3 or higher toxicity was reported in 6-16% of patients. With a 20 patient accrual goal, toxicity rates can be estimated to within 22% with 95% confidence. Any toxicity with at least 10% prevalence has at least an 87% chance of being observed. This design allows us to reasonably exclude a clinically significant increase in toxicity with the addition of radiation therapy to the durvalumab and tremelimumab combination as defined by the upper bound of the confidence interval.

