8.1.1 Screening Phase

Screening procedures will be performed up to 28 days before Day 1, unless otherwise specified. All subjects must first read, understand, and sign the IRB/REB/IEC-approved ICF before any study-specific screening procedures are performed. After signing the ICF, completing all screening procedures, and being deemed eligible for entry, subjects will be enrolled in the study.

Procedures that are performed prior to the signing of the ICF and are considered standard of care may be used as screening assessments if they fall within the 28-day screening window.

The following procedures will be performed during the Screening Visit:

- Informed Consent
- Review of eligibility criteria
- Medical history and demographics
- Complete physical exam
- ECOG Performance Status
- Vitals signs, weight
- 12-lead ECG (in triplicate [2-5 minutes apart])
- Archived tissue or tumor biopsy
- Review of prior/concomitant medications
- Imaging by CT/MRI
- Clinical laboratory tests for:
 - Hematology (see Table 3)
 - Clinical chemistry (see Table 4)
 - TSH with reflexive free T4
 - Coagulation (PT, aPTT, INR)
 - Creatinine Clearance
 - Serum or urine pregnancy test (for women of childbearing potential only)
 - Urinalysis (see Table 7)

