10.1 Safety Parameters

10.1.1. Definition of adverse events

The International Conference on Harmonization (ICH) Guideline for Good Clinical Practice (GCP) E6 (R1) defines an AE as:

Any untoward medical occurrence in a patient or clinical investigation subject administered a pharmaceutical product and which does not necessarily have a causal relationship with this treatment. An AE can therefore be any unfavorable and unintended sign (including an abnormal laboratory finding), symptom, or disease temporally associated with the use of a medicinal product, whether or not considered related to the medicinal product.

An AE includes but is not limited to any clinically significant worsening of a subject's pre-existing condition. An abnormal laboratory finding (including ECG finding) that requires an action or intervention by the investigator, or a finding judged by the investigator to represent a change beyond the range of normal physiologic fluctuation, should be reported as an AE.

Adverse events may be treatment emergent (ie, occurring after initial receipt of investigational product) or nontreatment emergent. A nontreatment-emergent AE is any new sign or symptom, disease, or other untoward medical event that begins after written informed consent has been obtained but before the subject has received investigational product.

Elective treatment or surgery or preplanned treatment or surgery (that was scheduled prior to the subject being enrolled into the study) for a documented pre-existing condition, that did not worsen from baseline, is not considered an AE (serious or nonserious). An untoward medical event occurring during the prescheduled elective procedure or routinely scheduled treatment should be recorded as an AE or SAE.

The term AE is used to include both serious and non-serious AEs.

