10.3.1 Study recording period and follow-up for adverse events and serious adverse events

Adverse events and serious adverse events will be recorded from time of administration of the first dose of investigational drug, throughout the treatment period and including the follow-up period (90 days after the last dose of durvalumab + tremelimumab).

During the course of the study all AEs and SAEs should be proactively followed up for each subject. Every effort should be made to obtain a resolution for all events, even if the events continue after discontinuation/study completion.

If a subject discontinues from treatment for reasons other than disease progression, and therefore continues to have tumor assessments, drug or procedure-related SAEs must be captured until the patient is considered to have confirmed PD and will have no further tumor assessments.

The investigator is responsible for following all SAEs until resolution, until the subject returns to baseline status, or until the condition has stabilized with the expectation that it will remain chronic, even if this extends beyond study participation.

Follow-up of unresolved adverse events

Any AEs that are unresolved at the subject's last visit in the study are followed up by the investigator for as long as medically indicated, but without further recording in the CRF. After 90 days, only subjects with ongoing investigational product-related SAEs will continue to be followed for safety.

AstraZeneca/MedImmune retains the right to request additional information for any subject with ongoing AE(s)/SAE(s) at the end of the study, if judged necessary.

Post study events

After the subject has been permanently withdrawn from the study, there is no obligation for the investigator to actively report information on new AE or SAEs occurring in former study subjects after the 90-day safety follow-up period for patients treated with durvalumab + tremelimumab. However, if an investigator learns of any SAEs, including death, at any time after the subject has been permanently withdrawn from study, and he/she considers there is a reasonable possibility that the event is related to study treatment, the investigator should notify the study sponsor and AstraZeneca/MedImmune Drug Safety.

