10.3.2 Reporting of serious adverse events

All SAEs will be reported, whether or not considered causally related to the investigational product, or to the study procedure(s). The reporting period for SAEs is the period immediately following the time that written informed consent is obtained through 90 days after the last dose of durvalumab + tremelimumab or until the initiation of alternative anticancer therapy. The investigator and/or Sponsor are responsible for informing the Ethics Committee and/or the Regulatory Authority of the SAE as per local requirements.

NOTE TO AUTHOR: For trials conducted in the United States, the following must be included (similar language must be included, referencing the appropriate health authority and reporting mechanism, for studies conducted outside of the United States). Note that all serious or unexpected adverse events must be reported to AstraZeneca regardless of the country where the study is conducted:

The investigator and/or sponsor must inform the FDA, via a MedWatch/AdEERs form, of any serious or unexpected adverse events that occur in accordance with the reporting obligations of 21 CFR 312.32, and will concurrently forward all such reports to AstraZeneca. A copy of the MedWatch/AdEERs report must be faxed to AstraZeneca at the time the event is reported to the FDA. It is the responsibility of the sponsor to compile all necessary information and ensure that the FDA receives a report according to the FDA reporting requirement timelines and to ensure that these reports are also submitted to AstraZeneca at the same time.

* A **cover page** should accompany the **MedWatch/AdEERs** form indicating the following:

- “Notification from an Investigator Sponsored Study”

- The investigator IND number assigned by the FDA
- The investigator's name and address
 - The trial name/title and AstraZeneca ISS reference number (ESR-16-11857)

* Sponsor must also indicate, either in the SAE report or the cover page, the ***causality*** of events ***in relation to all study medications*** and if the SAE is ***related to disease progression***, as determined by the principal investigator.

**** Send SAE report and accompanying cover page by way of email to AstraZeneca's designated mailbox:*** [contact]

If a non-serious AE becomes serious, this and other relevant follow-up information must also be provided to AstraZeneca and the FDA.

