11.2 Methods of statistical analyses

11.2.1 Safety Analyses

Safety and tolerability is the primary endpoint of this study, and all patients enrolled (including those replaced in the run in phase) will be assessed for this endpoint. Adverse events will be recorded and graded based on CTCAE v. 4, and their relationship to the experimental agents reported.

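### The primary toxicity analysis uses all enrolled patients as its denominator, so any patient enrolled but never dosed would lower the toxicity rate and its upper confidence bound

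*Combined protocol and SAP*

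**What the plan says.** All references are to the combined protocol and SAP.

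- **Analysis set.** Section 11.1 includes "All patients enrolled in the study, including those who were replaced in the run-in phase" in the analysis of both toxicity and efficacy. Section 11.2.1 makes safety and tolerability the primary endpoint and says that "all patients enrolled (including those replaced in the run in phase) will be assessed for this endpoint". Neither section requires a first dose. The abbreviation list expands SAS as safety analysis set, but Section 11 never defines one.
- **Point of enrolment.** Section 8.1.1: "After signing the ICF, completing all screening procedures, and being deemed eligible for entry, subjects will be enrolled in the study". This comes before Day 1.
- **Form of the summary.** The synopsis, under Statistical Methods and Data Analysis, has toxicities "summarized as the number and percentage of patients with each type of toxicity".
- **Yardstick.** Section 11.3 uses the upper confidence bound of the toxicity rate to exclude a meaningful rise in toxicity from adding radiation.
- **Start of event recording.** Section 10.3.1 says AEs and SAEs "will be recorded from time of administration of the first dose of investigational drug". Section 10.3.2 differs: "The reporting period for SAEs is the period immediately following the time that written informed consent is obtained". The Schedule of Study Assessments marks an AE/SAE assessment at screening. Section 10.1.1 defines a nontreatment-emergent AE as one that "begins after written informed consent has been obtained but before the subject has received investigational product".

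**The concern.** A toxicity rate should be a proportion of the patients exposed to the treatment. Under Sections 11.1 and 11.2.1, someone who passes eligibility, is enrolled and then deteriorates or withdraws before the first infusion adds one to the denominator. That person can add nothing to the numerator, because an event before dosing is by Section 10.1.1 nontreatment-emergent and so is not toxicity of the regimen.

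For a given number of events, the stated set can therefore move the rate and its upper bound only downwards, which is the favourable direction for a trial whose primary claim is safety. The plan does not say how an undosed patient is handled. The end of Section 4.2 says withdrawn patients are not replaced, so an incorrectly enrolled patient withdrawn before dosing would use one of the 20 places.

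**Working it through.** **Inputs.** Maximum enrolment is 20 (synopsis; Section 3.1). The confidence level is 95% and the decision quantity is the upper bound (Section 11.3). The number enrolled but never dosed, u, is not given. The values 0, 1, 2 and 4 below are assumptions, as are the event counts x.

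**Step 1: the plan's own figures.** Section 11.3 states precision within 22% and at least an 87% chance of seeing a toxicity of 10% prevalence.

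- Half-width at p = 0.5: 1.96 × √(0.25/20) = 21.9%, which matches.
- Detection: 1 − 0.9^20 = 87.8%, which matches.

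Both figures take all 20 patients as exposed.

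**Step 2: effect on the rate.** The plan reports x/20, while the rate among treated patients is x/(20 − u). The reported rate is thus the treated rate times (20 − u)/20: a factor of 1.00, 0.95, 0.90 and 0.80 for u = 0, 1, 2 and 4. With x = 4, 20.0% is reported where the treated rate is 21.1% (4/19), 22.2% (4/18) or 25.0% (4/16).

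**Step 3: effect on the upper bound.** The plan names no interval method, so the exact (Clopper-Pearson) two-sided 95% interval is used. Its upper bound is the 0.975 quantile of Beta(x + 1, n − x), with n = 20 − u.

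| u | n | x = 0 | x = 3 | x = 4 | x = 5 |
|---|---|---|---|---|---|
| 0 | 20 | 16.8% | 37.9% | 43.7% | 49.1% |
| 1 | 19 | 17.6% | 39.6% | 45.6% | 51.2% |
| 2 | 18 | 18.5% | 41.4% | 47.6% | 53.5% |
| 4 | 16 | 20.6% | 45.6% | 52.4% | 58.7% |

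The u = 0 row is what the plan would report whatever u is. The row for the true u is the bound among treated patients. For 3 to 5 events, the reported bound is too low by 1.7 to 2.1 points with one undosed patient and by 3.5 to 4.4 points with two.

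**Step 4: undosed patients on top of 20 treated.** If undosed run-in patients were replaced beyond the 20, the plan would report 4/21 = 19.0% (upper bound 41.9%) or 4/22 = 18.2% (40.3%), where the treated figure is 4/20 = 20.0% (43.7%). The direction is the same.

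**Step 5: what the denominator does not touch.** The run-in decision turns on two or more DLTs, and Section 6.4 replaces patients who leave early without one. The stopping rule in Section 3.3 counts patients with Grade 4 or higher drug-related toxicity. Neither divides by the number enrolled.

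**The case against.** The strongest reply is that the plan expects every enrolled patient to be treated. The synopsis and Section 3.1 say so. The parenthesis in Section 11.1 points to Section 4.4, whose example of a replaced patient is one whose infusion was cut short by a reaction. The evident purpose is to keep partly exposed patients in the safety analysis, which is right. This stands as a statement of intent, and it means the dilution may turn out to be zero. It does not remove an undosed patient from the denominator that the plan prescribes. Under the Schedule of Study Assessments, safety blood results must still be reviewed before an infusion starts, so enrolment does not guarantee dosing.

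Four stronger readings are tempting, and the documents do not support them.

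- *An undosed patient can have no recorded event at all.* Section 10.3.1 alone suggests this, but Section 10.3.2, the screening column of the schedule and Section 10.1.1 all provide for pre-dose events. The argument rests on such events not being treatment toxicity.
- *The reported rate is biased low as a matter of fact.* It is so only if someone is enrolled and not dosed.
- *The analysis set weakens the 87% detection figure.* With 18 treated, the chance is 1 − 0.9^18 = 85.0%, but that loss comes from treating fewer patients. It is the same under either denominator, and the fix does not restore it.
- *A safety decision would change.* The count-based rules are untouched. With no events, one undosed patient moves the bound from 16.8% to 17.6%, across the 17% Grade 3-4 rate cited in Section 11.3. That section does not set 17%, or any other figure, as a limit.

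**Conclusion.** The point holds in conditional form. The plan states a denominator for its primary endpoint that includes patients who cannot have the outcome, and the error can run only in the favourable direction.

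The size is modest: about 2 points on the exact 95% upper bound per undosed patient at 3 to 5 events, set against an interval of 5.7% to 43.7% for 4/20. It is zero if all enrolled patients are dosed. These figures rest on assumed numbers of events and undosed patients and on the exact interval. The direction does not depend on those choices once at least one patient is undosed. The change is worth making because the set should be fixed before the data are known.

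The differing start dates for SAE recording in Sections 10.3.1 and 10.3.2 are a separate inconsistency that needs reconciling. Settling it either way would not repair the denominator.

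**What to change.** In Sections 11.1 and 11.2.1, define the safety set as all patients who received any amount of durvalumab or tremelimumab, including replaced run-in patients. Use it for every toxicity rate and confidence bound. Keep all enrolled patients for efficacy, as Section 11.2.2 has it. Report separately how many patients were enrolled but never dosed, and list any events they had.

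Reconcile Sections 10.3.1 and 10.3.2 so that one start of SAE recording applies throughout.

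The cost is about one sentence in each of the two analysis sections, plus the edit to the recording period. The reported toxicity rate may be slightly less favourable. No visit, treatment or sample size changes, and if every enrolled patient is dosed the toxicity results are identical.

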11.2 Methods of statistical analyses

11.2.1 Safety Analyses

Safety and tolerability is the primary endpoint of this study, and all patients enrolled (including those replaced in the run in phase) will be assessed for this endpoint. Adverse events will be recorded and graded based on CTCAE v. 4, and their relationship to the experimental agents reported.

11.2.2 Efficacy Analyses

All patients enrolled in the study (i.e. the initial 6 patient cohort, and the additional 14 patient expansion) will be included in the efficacy analyses. Clinical responses to the combination of durvalumab, tremelimumab and hypofractionated radiation will be based on RECIST 1.1 criteria. Oncologic outcome endpoints such as progression free and overall survival will be calculated from the date of study enrollment, until disease progression or death from any cause, respectively. Survival estimates will be calculated using the Kaplan-Meier method.

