Subjects may withdraw consent at any time for any reason or be dropped from the trial at the discretion of the investigator should any untoward effect occur. In addition, a subject may be withdrawn by the investigator or the Sponsor if enrollment into the trial is inappropriate, the trial plan is violated, or for administrative and/or other safety reasons.

Subjects who are permanently discontinued from receiving investigational product will be allowed for safety per Appendix 2 or 3, including the collection of any protocol-specified blood specimens, unless consent is withdrawn or the subject is lost to follow-up or enrolled in another clinical study. All subjects will be followed for survival. Subjects who decline to return to the site for evaluations will be offered follow-up by phone every 3 months as an alternative.

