The investigator or qualified designee will review all new anti-neoplastic therapy initiated after the last dose of trial treatment. If a subject initiates a new anti-cancer therapy within 30 days after the last dose of trial treatment, the 30 day Safety Follow-up visit must occur before the

first dose of the new therapy. Once new anti-cancer therapy has been initiated the subject will move into survival follow-up.

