9. DISEASE EVALUATION AND METHODS

The response to immunotherapy may differ from the typical responses observed with cytotoxic chemotherapy including the following (Wolchok et al 2009, Nishino et al 2013):

- Response to immunotherapy may be delayed
- Response to immunotherapy may occur after PD by conventional criteria
- The appearance of new lesions may not represent PD with immunotherapy
- SD while on immunotherapy may be durable and represent clinical benefit.

Based on the above-described unique response to immunotherapy and based on guidelines from regulatory agencies, e.g., European Medicines Agency's "Guideline on the evaluation of anti-cancer medicinal products in man" (EMA/CHMP/205/95/Rev.4) for immune modulating anti-cancer compounds, the study may wish to implement the following in addition to standard RECIST 1.1 criteria:

- RECIST will be modified so that PD must be confirmed at the next scheduled visit, preferably, and no earlier than 4 weeks after the initial assessment of PD in the absence of clinically significant deterioration. Treatment with durvalumab + tremelimumab would continue between the initial assessment of progression and confirmation for progression.
- In addition, subjects may continue to receive durvalumab + tremelimumab beyond confirmed PD in the absence of clinically significant deterioration and if investigators consider that subjects continue to receive benefit from treatment.

Modification of RECIST as described may discourage the early discontinuation of durvalumab + tremelimumab and provide a more complete evaluation of its anti-tumor activity than would be seen with conventional response criteria. Nonetheless, the efficacy analysis will be conducted by programmatically deriving each efficacy endpoint based on RECIST 1.1 criteria.

Of note, clinically significant deterioration is considered to be a rapid tumor progression that necessitates treatment with anti-cancer therapy other than durvalumab + tremelimumab or with symptomatic progression that requires urgent medical intervention (e.g., central nervous system metastasis, respiratory failure due to tumor compression, spinal cord compression).>>

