9.1 Progression free and Overall survival

Data on disease progression by RECIST criteria, and patient death will be recorded and used to calculate PFS and OS. Patients who have discontinued study therapy due to disease progression, toxicity, or withdrawal of consent will continue to be followed to collect data for this endpoint.

Subjects who have disease control following completion of 12 months of treatment or subjects who are withdrawn from durvalumab + tremelimumab treatment for reasons other than confirmed PD will continue to have objective tumor assessments (see Appendix 3).

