10.3.2.1 Reporting of deaths

All deaths that occur during the study, or within the protocol-defined 90-day post-last dose of durvalumab + tremelimumab safety follow-up period must be reported as follows:

- Death that is clearly the result of disease progression should be documented but should not be reported as an SAE.
- Where death is not due (or not clearly due) to progression of the disease under study, the AE causing the death must be reported to as a SAE within **24 hours** (see Section 10.3.2 for further details). The report should contain a comment regarding the co-involvement of progression of disease, if appropriate, and should assign main and contributory causes of death.
- Deaths with an unknown cause should always be reported as a SAE.

Deaths that occur following the protocol-defined 90-day post-last-dose of durvalumab safety follow-up period will be documented as events for survival analysis, but will not be reported as an SAE.

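### Section 11.2.2, read literally, ends PFS at progression and does not count a death before documented progression; Section 9.1 suggests a composite, but no passage states one.

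*Combined protocol and SAP*

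**What the plan says.** Three places describe how PFS is calculated.

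- **Section 11.2.2 (Efficacy Analyses)** is the only text that assigns an event to each endpoint: "progression free and overall survival will be calculated from the date of study enrollment, until disease progression or death from any cause, respectively". It then names the Kaplan-Meier method. It gives no rule for a patient who dies without documented progression.
- **Section 9.1** describes the data: "Data on disease progression by RECIST criteria, and patient death will be recorded and used to calculate PFS and OS". Both kinds of event are listed against both endpoints, with no one-to-one pairing.
- **Synopsis, Statistical Methods and Data Analysis** leaves the event open: "Outcomes will be calculated from the date of study entry to the date of the corresponding event".

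Section 10.3.2.1 adds that deaths after the 90-day safety period "will be documented as events for survival analysis, but will not be reported as an SAE", without saying whether that covers PFS, OS or both.

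PFS is a secondary objective (Section 2.1.2). Section 11.3 sets no numeric target for it. It does say that either objective responses or encouraging PFS in the 20 patients would justify a larger study.

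**The concern.** The pairing in Section 11.2.2 describes time to progression under the name of PFS. An analyst who programs the endpoint from that sentence would not count a patient who dies before progression is documented. The natural Kaplan-Meier treatment of that patient is then censoring at death, which assumes that the patient would have gone on like those still under observation. A fatal toxicity before the first scan would leave no mark on the PFS curve when it happened, and it would raise every later estimate relative to counting it.

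The judgement at stake is whether to go on to a larger study. There is no control arm and no threshold, so how the PFS curve looks depends directly on how the event is defined.

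**Working it through.** **1. The texts side by side**

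| Place | Event for PFS | Death without progression |
|---|---|---|
| Section 11.2.2 | progression (by the pairing) | not an event as written; no censoring rule |
| Section 9.1 | progression and death data both used | composite suggested, not stated |
| Synopsis | unspecified corresponding event | silent |
| Section 10.3.2.1 | survival analysis, endpoint not named | silent as to PFS |

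No passage says progression or death, whichever comes first. Section 9.1 can be read as a composite, or as progression for PFS and death for OS. This is an ambiguity, not a flat contradiction.

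**2. Can such deaths occur under the planned follow-up?**

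On-treatment scans are 8 weeks apart, plus or minus 1 week (Schedule of Study Assessments, footnote k). After completion with disease control, or after stopping for toxicity, they are 8 to 12 weeks apart until confirmed progression (Appendix 2). Section 4.3 allows a lighter route: "Subjects who decline to return to the site for evaluations will be offered follow-up by phone every 3 months as an alternative". It also says "All subjects will be followed for survival", so a death may be known where progression is not.

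The documents give no rate for deaths without documented progression. For scale only, Sections 1.4.2.3 and 1.1.5 report treatment-related fatal events in 2 of 102 lung cancer patients on the drug combination (2/102 = 2%) and 1–5% mortality with SBRT re-irradiation. Applied as an assumption to 20 patients, the chance of at least one such death is:

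- at 1%: 1 − 0.99^20 = 0.18
- at 2%: 1 − 0.98^20 = 0.33
- at 5%: 1 − 0.95^20 = 0.64

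Populations differ, and some of these deaths could follow progression.

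**3. Effect of one death**

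A death with k patients at risk contributes (k−1)/k to the Kaplan-Meier product if counted and 1 if censored. The patient leaves the risk set either way, so all later estimates differ by exactly k/(k−1):

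- k = 20: 20/19 = 1.05
- k = 10: 10/9 = 1.11
- k = 5: 5/4 = 1.25

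**4. Effect of several early deaths**

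Input from the documents: n = 20. Assumption: d deaths before the week-8 scan, with no earlier progression or censoring. The factor is 20/(20−d).

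| d | Factor | True 50% reads | True 30% reads |
|---|---|---|---|
| 0 | 1.000 | 50.0% | 30.0% |
| 1 | 1.053 | 52.6% | 31.6% |
| 2 | 1.111 | 55.6% | 33.3% |
| 3 | 1.176 | 58.8% | 35.3% |
| 4 | 1.250 | 62.5% | 37.5% |

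**5. Two direct checks on assumed event patterns**

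- Two deaths, then 8 progressions at week 8. Deaths counted: 10/20 = 0.500. Deaths censored: 10/18 = 0.556. The two patients carried forward as progression-free: 12/20 = 0.600.
- Ten progressions at week 8, one death at week 12 with 10 at risk, 3 progressions at week 16. Counted: (10/20)(9/10)(6/9) = 0.300. Censored: (10/20)(6/9) = 0.333. The ratio is 1.11 = 10/9.

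**6. Scale against sampling error**

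The plan states no PFS figure. Its toxicity precision figure in Section 11.3 reproduces: 1.96 × √(0.5 × 0.5/20) = 0.219, against a stated 22%. The same half-width applies to a proportion of 50% for PFS. The largest shift at 50% in the table is 62.5 − 50 = 12.5 points, which is below it.

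**The case against.** The strongest reply is that this is loose drafting. The endpoint is called progression free survival, Section 9.1 names both kinds of event, and an experienced analyst would count deaths. Bias then needs three things together: the pairing is followed literally, the deaths are not counted, and such deaths occur. That is fair on likelihood. It does not repair the text, because the only sentence that assigns events gives the wrong one for PFS and Section 9 says that efficacy endpoints will be derived by program.

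The second reply also has force. Section 9.1 keeps following patients who stop for progression, toxicity or withdrawal of consent. It continues tumour assessments in those withdrawn for reasons other than confirmed progression, and Appendix 2 schedules the scans. This limits deaths without documented progression. It cannot remove them while scans are weeks apart, visits can be declined and a toxicity can be fatal before progression.

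The third reply concerns weight. PFS is secondary and descriptive, has no test or threshold, and is one of two alternative grounds for a larger study. The other, objective response, is untouched. All of this stands.

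A reader might infer more than the documents support:

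- **That scanning stops when new treatment starts.** Section 6.1.1 says "Once new anti-cancer therapy has been initiated the subject will move into survival follow-up", but not that tumour assessments end. How new therapy enters the PFS analysis is a separate question.
- **That the progression date is also undefined.** Section 9 says "PD must be confirmed at the next scheduled visit, preferably, and no earlier than 4 weeks after the initial assessment of PD", but adds this to standard RECIST 1.1 and then bases the efficacy analysis on RECIST 1.1, which largely answers the question.
- **That the plan sets out to hide deaths.** Deaths are recorded, all subjects are followed for survival, and OS counts every death.

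**Conclusion.** The concern holds as a defect in the wording. As written, Section 11.2.2 makes PFS a time-to-progression endpoint, and no other passage states the composite that was probably meant.

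The consequence is conditional. If deaths without documented progression occur and are censored, PFS is biased upward by k/(k−1) per death. With one to four early deaths among 20, a true 50% reads as about 53% to 63%. The number of deaths and their timing are assumptions, and zero deaths gives no bias. The shift is smaller than the half-width of about 22 points but, unlike sampling error, it always runs in the favourable direction.

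The primary safety conclusion, OS, the response rate and the sample size are unaffected. The point should be corrected, but it does not threaten the trial's main result.

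**What to change.** In Section 11.2.2, replace the paired sentence with two definitions:

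- PFS: time from enrolment to the first of RECIST 1.1 progression or death from any cause, with patients alive and without progression censored at their last tumour assessment.
- OS: time from enrolment to death from any cause.

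Bring Section 9.1 and the statistical paragraph of the synopsis into line. Report the number of deaths without documented progression beside the PFS curve, so that a reader can see how much the definition matters.

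The cost is a few sentences in three places. No new data, scans, visits or patients are needed, because progression and death are already recorded and all subjects are followed for survival. The one downside is that PFS may look slightly less favourable.
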